# 5.4 Education phase

Between the pre-intervention and intervention phases of the study, staff members of the study hospital units will be alerted to the function and location in the EHR of the report card. Written material including the same information and research team contact information will be left in the breakrooms of these units and disseminated by email. Research team members will answer any questions and record any concerns. All staff comments and concerns will be recorded completely anonymously. Research team members will review these comments and concerns to determine if any modifications to the intervention or clarification to the educational material is required. During this period, the report card will be marked as in-testing.

# **6 Monitoring**

### 6.1 Adverse event and safety monitoring:

No data safety monitoring committee is planned for this sub-study due to the non-significant risk and pilot nature. No external safety monitor is planned, though all adverse events will be reported to NCATS (funder of the study).

### **6.2 Interim Analyses**

No formal interim analyses are planned.

#### 6.3 Harms

The postoperative provider survey will include a link and phone number to contact the research coordinator if they believe a serious adverse event or near miss occurred related to the ACT-postoperative communication. As an example, they may believe that ML risk estimates were sent for the incorrect patient. Our communications will all include the role of the ML predictions as advisory, and that the responsibility for decision making lies with the provider. These will be reported to the WUSTL IRB. Descriptive statistics related to uncommon potential harms will be included in the trial reporting.

### 6.4 Auditing

Auditing will consist of debriefing interviews and surveys described above.

### 7 Ethics and Dissemination

## 7.1 Ethics review approval

This study has been submitted to the Human Research Protection Office at Washington University (St. Louis, MO). This study will be registered at clinicaltrials.gov.

#### 7.2 Protocol Amendments

Any modifications to the protocol which may impact on the conduct of the study, potential benefit of the patient or may affect patient safety, including changes of study objectives, study design, patient population, sample sizes, study procedures, or significant administrative aspects will require a formal amendment to the protocol. Such amendment will be agreed upon by the WUSTL IRB. As discussed above, small changes to the ACT report template are anticipated and will not be regarded as protocol modifications.

### 7.3 Consent

A waiver of informed consent for patients is requested.

1) The study presents non-significant risk to participants. The report card is not intended as an implant and presents no potential for serious risk to the health, safety or welfare of a subject. The report card is not purported or represented to be for use supporting or sustaining human life. The report card is not being used for substantial importance in diagnosing, curing, mitigating, or treating disease or otherwise preventing impairment of human health. Treating physicians retain control over all therapies, and no specific therapies are recommended. The warning may at most "drive" clinical management. The conditions predicted in PACU are not generally life-threatening and providers have time to correct any errors that they make. The ACT clinician will screen out grossly incorrect alerts. The educational sheet presented prior to the report card will remind providers that the report card is intended to cause them to seek out additional information and draw their own conclusions about the best course of action for a particular patient; it is not an alarm intended to provoke immediate clinical action.

There is no obvious mechanism for physical, psychological, financial, or legal harm. Patients in the usual care (non-contact) period remain in the current standard of care with critical-care level oversight by physicians and nurses in phase-one recovery. It is unlikely that physicians would take harmful action based on the information in the contact-arm report as it does not recommend specific actions. Because the education for providers will include the ~50% sensitivity of the alert, they will be aware not be falsely

- reassured by the absence of an alert
- As documented above, the minimal necessary amount of information about subjects is collected, and best practices are used to secure it.
- 2) The project is not scientifically feasible without a waiver of consent. At the time when eligibility can be determined, the patient has undergone anesthesia or sedation, and would need to have been consented in preop (or preferably sooner). Difficulty with obtaining same-day consent would lead to a much more selected population and not answer the pragmatic scientific question. It would also lead to a much slower recruitment, making it likely that the trial would fail to complete in a timely fashion and "wasting" the effort.
- 3) Because of the need to link intraoperative risk models to patient locations and outcomes, it is not possible to conduct it without identifiable private information.
- 4) The waiver will not affect the rights or welfare of the participants. As the Secretary's Advisory Committee on Human Research Protections notes in 2008, this requirement related to any other legal consent requirements, which are not present in this case. Additionally, we should consider if the population would object to the waiver if informed of it or believe that it could cause them harm. We believe that due to the novel nature of the technology, standard-of-care control arm, minimal risk, and diversity of successful PACU staffing models participants would not object to participation.
- 5) There are no special circumstances necessitating post-facto information provision to the patient. This requirement is intended for research involving deception.

A participation document will be included at the beginning of the workday for PACU physicians and postoperative providers receiving messages describing the study.

A partial waiver of informed consent for providers is requested. Providers are exposed to the report card and may optionally complete the above survey reporting inaccurate data. Because (1) surveys do not collect identifying information and participation requires active effort, (2) predicting the applicable providers is impossible, separate consent forms will not be obtained and we request a waiver of consent. Study information is included in the survey link which includes that their participation is completely voluntary, that no communication is made to the institutional leadership, and that all stored information is anonymized to the extent possible.

- 1) The study presents non-significant risk to participants. Survey responses are securely stored and contain no identifying information. Providers can skip the survey without any harm
- 2) The project is not scientifically feasible without a waiver of consent. Because the midlevel and nursing providers for this subset of patients are not knowable ahead of time, we would need to consent every possible nurse and midlevel provider.
- 3) No identifiable private information is requested.
- 4) There is no foreseeable effect on the rights or welfare of the participants. Because it is unidentified, there is no mechanism for (non) participation to affect the providers.
- 5) There are no special circumstances necessitating post-facto information provision to the patient. This requirement is intended for research involving deception.

For direct handoff observations, participants will be approached and provided with study information before handoff begins. We will identify the relevant OR cases and approach the OR staff during emergence from anesthesia. Because the participating PACU and ward nurse is impossible to identify ahead of time (these are assigned throughout the day), we will approach and ask for written consent shortly before handoff begins. We will attempt to approach the pool of PACU nurses with study information during the morning of days on which we plan direct

observations, with the goal of having discussed the study with participants before the patient arrives.

Because many PACU nurse to ward nurse handoffs occur over phone calls, having obtained consent to observed the handoff observation from the PACU nurse, we will disclose our observation of the PACU nurse to any party on the phone, allowing them to request privacy if needed.

No consent will be recorded for the education phase in which we notify staff members how to use the intervention as all information collected in that phase is completely anonymous.

Because of the nature of the intervention. no provisions are made for ancillary post-trial care or participants who are harmed. Participants will receive appropriate care at BJH prior to discharge.

### 7.4 Confidentiality

Identifying data will be protected, as described above.

#### 7.5 Declaration of interests

The investigators have no financial conflicts of interest.

#### 7.6 Dissemination

We will disseminate the results with presentations to relevant stakeholder groups, peer-reviewed publications, and national meetings. We will also use the BJC Collaborative as a vehicle for dissemination.

### 7.7 Data Sharing Policy

Data from the ODIN-Pilot trial will be made available for analysis in compliance with the recommendations of the ICMJE. Individual participant data that underlie the results of the trial will be made available after appropriate de-identification, along with the study protocol and statistical analysis plan. We plan to make this information accessible to researchers who provide a methodologically appropriate proposal for the purpose of achieving the aims of that proposal. Data will be available beginning 9 months and ending 36 months following trial publication at a third-party website. Data requestors will need to sign a data access agreement to gain access to trial data. Proposals should be directed to [contact].

This protocol was written in compliance with the SPIRIT Checklist Guidelines for Interventional Trials.

## 7.8 Pandemic Infectious Risks to Participants and Study Personnel

The study has very little to no implications for exposure to sars-cov-2 infection.

The only study personnel on-site are those doing direct observations of handoffs. The study personnel will be screened by universal policy before entry to BJH, use appropriate face coverings, and practice physical distancing. During obtaining consent to observe, hand hygiene will be observed with disposable pens and paper records stored in a daily "used documents" cardboard folder to minimize accidental fomites. During observation of handoff the assistant will maximize physical distance while being able to overhear the conversation. This activity will not continue during any time of increased community transmission (e.g. cancellation of elective surgery).

The personnel in the ACT, PACU providers, and wards providers are all present at BJH as part of their usual clinical activity with no modification. Individuals are contacted only over telephone. Electronic informed consent is used, creating no additional risk of exposure.

Patients are exposed to no increased risk of exposure; no study personnel directly interact with the patient.

Appendix: Handoff Direct Observation Guide
Global Rating of Handover Effectiveness
[] Not at all effective
[] Somewhat effective
[] Moderately effective
[] Very effective
[] Extremely effective
Content and organization of handoff was
[] Very disorganized and unclear
[] Somewhat disorganized and or irrelevant
[] Moderate relevance and organization
[] Mostly relevant and organized
[] Very well organized and very effective delivery
Content and Completeness
[] No aspects of SBAR adequately covered
[] Some but not all critical content
[] All critical content (minimally sufficient)
[] All critical and most SBAR items
[] All SBAR and pertinent info, very thorough
Confirmation and comprehension
[] No questions or concerns raised or addressed

[] Questions or concerns not adequately addressed
[] Moderate confirmation of comprehension
[] Adequately addressed concerns and questions
[] All questions and issues fully addressed
Level of Engagement
[] None
[] Brief engagement by one or both sides, but mostly inattentive
[] Moderate: no negative impact on quality
[] Both sides engaged throughout handover
[] Ideal engagement

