# **Non-Technical Summary**

Although surgery and anesthesia have become much safer on average, many patients still experience complications after surgery. Some of these complications are likely to be avoided or less severe with early detection and treatment. Barnes-Jewish Hospital has recently started using an Anesthesia Control Tower (ACT), which is a remote group lead by an anesthesiologist who reviews live data from BJH operating rooms and calls the anesthesia provider with concerns to improve reaction times and improve use of best-practices treatments. The ACT also uses machine learning (ML) to calculate patient risks during surgery as a way of measuring when the patient is doing better or worse.

We think that many times the right interpretation of the data or the right treatment to give isn't clear until the surgery is nearly finished. The medical team in the recovery room (post-anesthesia care unit, PACU) and surgical wards is responsible for deciding the treatment strategy, but they don't have all the information available from the intraoperative monitors and events. The patient may still be too sedated or confused from the anesthesia to explain much about their preoperative history. Our goal is to use ML to create a report card for each patient that summarizes the preoperative assessment and intraoperative data in a way that is useful for postoperative providers. In addition to communicating specific facts and risks, the report card may cause the postoperative provider to ask different questions at handoff and spend more time with vulnerable patients.

The goal of this study is to integrate these ML reports into the clinical workflow and to determine if it does affect handoff behavior. The screened patients will be all adults having surgery at BJH with the division of Acute and Critical Care Surgery, Otolaryngology, Hepato-biliary Surgery, and Abdominal Transplant Surgery with elevated risk of unplanned ICU admission. Exclusion criteria are a planned ICU admission or outpatient surgery (no hospital admission).

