Communicating from the ACT to the PACU physicians presents several advantages. First, the ACT clinician is familiar with the general model of ML output generated by AlertWatch and will filter out obvious errors from reaching the care team and potentially harming the patient, minimizing risk to participants. Second, because on a given day a single attending physician and resident oversees the PACU at BJH South Campus, friction related to communication between the ACT and these providers will be minimized as these contacts become routine. Both parties will have the opportunity to rapidly adjust to the presence of the report card as they will process multiple such reports per day. Third, because the ACT-postop communication happens before formal handoff, it will allow these providers to look into higher risk cases before they arrive and ask more detailed questions during handoff. We anticipate that most interactions will consist of simply forwarding the report card. The ACT will not communicate directly to PACU nurses or ward providers.

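### The observation guide's confirmation-and-comprehension item has no level for a clear handoff that needed no questions and, read literally, ranks it lowest

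*Combined protocol and SAP*

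**What the plan says.** The appendix guide has five items with five options each. The first option of the confirmation-and-comprehension item is "No questions or concerns raised or addressed". The second option reads "Questions or concerns not adequately addressed", the third option reads "Moderate confirmation of comprehension", the fourth option reads "Adequately addressed concerns and questions" and the last option reads "All questions and issues fully addressed". The other four items start at the poor end; the global rating, for example, opens with "Not at all effective". The guide prints no numeric scores, offers no not-applicable box and gives no rating instructions.

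Questions are part of how the card is expected to work. The Non-Technical Summary says "the report card may cause the postoperative provider to ask different questions at handoff". Section 4.3.1, on early contact between the control tower and the PACU physicians, says "it will allow these providers to look into higher risk cases before they arrive and ask more detailed questions during handoff". The survey in section 4.4.1 asks users of the card how far it altered the questions asked or the information passed on.

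Section 4.4.2 lists direct observation of up to 150 handoffs under secondary outcomes. Section 1 says that direct observations, along with interviews and structured tools, will be used to validate the provider survey. Section 5.3 gives no scoring or analysis for the guide.

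**The concern.** An observer who takes the options at face value, in the order of the rest of the form, has to place a complete handoff that prompted no questions in the bottom box. A handoff in which a question was asked and left hanging goes one box higher. The bottom box therefore mixes two different events: a receiver who never showed understanding, and a receiver who had nothing left to ask.

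This matters more here than on a general-purpose form because the intervention is expected to act on questions. If the card changes how often a handoff passes without any, the item changes too, whether or not comprehension does. The primary outcome is self-reported (section 4.4.1) by clinicians who know the day type (section 4.9), and the observation form is one of the few checks on it. An item that follows question-asking could seem to support or contradict the survey for reasons unrelated to handoff quality.

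**Working it through.** The plan states no figure for this item, so there is none to reproduce. The check is a reading of the options, followed by an illustration on assumed inputs.

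**Step 1: what each option turns on.**

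| Position | Option | What decides it |
|---|---|---|
| 1 | "No questions or concerns raised or addressed" | whether anything was raised or addressed |
| 2 | "Questions or concerns not adequately addressed" | something was raised, poorly handled |
| 3 | "Moderate confirmation of comprehension" | comprehension; questions not mentioned |
| 4 | "Adequately addressed concerns and questions" | something was raised, handled adequately |
| 5 | "All questions and issues fully addressed" | something was raised, handled fully |

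Only the step from 1 to 2 depends on whether a question or concern arose. A clear handoff with none fits position 1 literally. It might be put at position 3 if the observer treats a read-back as confirmation. No option describes it directly, and positions 4 and 5 presuppose something to address.

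**Step 2: direction of the scale.** This is inferred. The other four items run from worst to best, and positions 2 to 5 of this one also improve, so position 1 is taken as the lowest.

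**Step 3: how far question-asking alone could move the item.** Code the positions 1 to 5. Let d be the share of handoffs that move from no questions to some questions, u the mean rating of those handoffs before the move, and v their mean rating after it. With all other handoffs unchanged,

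shift in item mean = d × (v − u).

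The documents give none of these quantities. Every input below is an assumption.

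| No-question share | d | u | v | Shift |
|---|---|---|---|---|
| 40% to 25%, new questions unresolved | 0.15 | 1 | 2 | 0.15 × 1 = 0.15 |
| 40% to 25%, new questions mostly well handled | 0.15 | 1 | 3.7 | 0.15 × 2.7 = 0.405 |
| 20% to 10%, or 50% to 40% | 0.10 | 1 | 3 to 4 | 0.20 to 0.30 |
| 40% to 20% | 0.20 | 1 | 3 to 4 | 0.40 to 0.60 |
| 40% to 25%, half of no-question handoffs rated 3 | 0.15 | 2 | 3.7 | 0.15 × 1.7 = 0.255 |
| 25% to 40% (card reduces questions) | −0.15 | 1 | 2 to 3.7 | −0.15 to −0.405 |

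The value 3.7 is the mean when positions 2 to 5 have shares of 10, 30, 40 and 20%: 0.2 + 0.9 + 1.6 + 1.0 = 3.7.

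The first row shows the fault most plainly: handoffs that were clear become handoffs with unresolved questions, and the item improves by 0.15.

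**Step 4: the same moves if a clear no-question handoff is rated as adequate.** Take u = 4. The first row becomes 0.15 × (2 − 4) = −0.30, so the item falls when questions go unresolved. The second becomes 0.15 × (3.7 − 4) = −0.045, close to no change.

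**The case against.** Four points can be made for the form as it stands.

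- **The wording is less rigid than it looks.** A reader might infer that every handoff without questions must get the bottom rating. The text does not support that: option 1 also covers concerns, which the giving side can raise and deal with, and option 3 can take a read-back without questions. This stands, but it leaves the choice to each observer.
- **The item still grades comprehension.** A reader might infer that it measures question-asking instead. That goes too far: options 2, 4 and 5 grade how well matters were addressed, and option 3 names comprehension. Since an observer can see only outward confirmation, ranking its absence lowest is defensible. What is missing is a way to separate that absence from having nothing to ask.
- **The direction is not fixed.** A reader might infer that the item must rise on card days. The documents speak of different and more detailed questions, not of fewer handoffs without any. The section 4.3.1 statement concerns PACU physicians, while section 4.4.2 also covers PACU-to-ward handoffs. The card goes to the anesthesia team as well, and the example card suggests adding plan and assessment to the handoff, which could make questions fewer. This stands in full.
- **Little depends on it.** It is one of five items on a secondary form with no planned summary score or test. The survey question about having all needed information corresponds more closely to the content-and-completeness item. This stands, and it lowers the priority.

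**Conclusion.** The point holds as a minor one. The item has no level for a clear handoff in which nobody needed to raise a question. Read literally, and in the order of the other items, it puts that handoff below one whose questions were not adequately addressed. Because the card is expected to change the questions asked, the item can differ between with- and without-intervention days through question-asking alone.

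Direction and size are unknown. The illustrative shifts, from 0.15 to 0.60 points upward or the reverse if questions become fewer, rest on assumed no-question shares, assumed 1-to-5 coding and, in most rows, every no-question handoff being rated 1. They show that the mechanism is possible and are not estimates for this trial. No false-positive rate is attached, because the plan specifies no test for this item and no split of the observed handoffs by day type. The primary outcome is not affected.

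**What to change.** Before phase 3 observations:

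1. Add a separate yes/no field for whether any question or concern was raised. This is useful in its own right as a process measure of the expected mechanism.
2. Add an anchor or a written rater rule under which a handoff with no questions needed and understanding confirmed by the receiver is rated as adequate. Reserve the lowest level for no confirmation of comprehension.

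If the item wording must stay unchanged, keep the added yes/no field and report the item separately by its value. Where no questions were raised, do not use the item as evidence for or against the survey's validity.

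The cost is one tick box and a line of guidance. The downside of changing the anchors is a small loss of comparability with forms already completed, or with a source instrument if there is one; the documents do not say. The unchanged-wording option avoids that loss.
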